#### 5.2 Inclusion/exclusion criteria

#### Phase 2 Inclusion Criteria:

- 1. Age 18 to 90.
- 2. Confirmed COVID-19 diagnosis
- At least one of the following: ① Respiratory distress, RR ≥ 30 breaths/min without oxygen; ② Partial arterial oxygen pressure (PaO2) / Fraction of inspiration O2 (FiO2) >100 <300mmHg (1mmHg = 0.133kPa).

- 4. Chest imaging confirms lung involvement and inflammation.
- Inflammatory status as documented by at least one of the following: Lactate dehydrogenase (LDH) > normal range, C-reactive protein (CRP) ≥ 100mg/L or IL-6 ≥ 40pg/mL, serum ferritin ≥ 900ng/mL, XDP >20mcg/mL.

Phase 3 Inclusion Criteria: same as above; other criteria TBD based on Phase 2 outcomes.

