4.8 Handling of missing and incomplete data

The number of subjects with missing data will be presented under the "Missing" category, if present. Missing values will not be included in the denominator count when computing percentages. Similarly, only the non-missing values will be evaluated for computing summary statistics for continuous endpoint. Any exception will be clarified as a note.

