At each time point the number and proportion of patients within each class (Severe, Moderate, or Mild for PaO₂/FiO₂; Invasive, High Flow, or Low Flow for the type of support) will be provided.

Finally, summary of cumulative quantity (L) and cumulative duration (hours) of oxygen treatment will be performed at 7 days and subsequent time points considering the variable as continuous.

7.2.2.6 *Incidence and duration of mechanical ventilation use*

Number and proportion along with the 95% confidence interval (Clopper-Pearson's formula) of subjects requiring mechanical ventilation will be calculated and compared.

Comparison between treatments in cumulative duration (hours) of mechanical ventilation will be performed at 7 days and subsequent time points considering the variable as continuous. Analysis will be performed overall and stratified by Invasive/Non-invasive mechanical ventilation.

7.2.2.7 *Incidence of ICU admission need*

Number and proportion along with the 95% confidence interval (Clopper-Pearson's formula) of subjects requiring ICU admission will be calculated and compared.

Comparison between treatments in duration (days) of ICU stay will be performed considering the variable as continuous.

7.2.2.8 *Change from baseline in lung damage extension and lung exudation degree (assessed by Chest CT or Rx)*

The comparison of the clinical evaluation of lung damage extension and lung exudation between the two study treatment arms will be performed by means of Wilcoxon signed-rank test.

7.2.2.9 *Respiratory parameters*

Change from baseline of FiO₂, Respiration rate, PaO₂, SpO₂ and PaO₂/FiO₂ will be compared between treatments considering the continuous nature of these variables.

7.2.2.10 *CRP and Hs-CRP*

CRP (mg/L) and Hs-CRP (mg/L) will be compared between treatments considering their continuous nature.

7.3 **Analysis of exploratory efficacy endpoints**

Explorative endpoints (section 3.5.3) will be analyzed at each available time points by means of descriptive statistics. Specifically, analyses will be provided for baseline visit, each post-baseline visit, and the change from baseline measurements to each visit. Comparison between treatments will be performed by means of two-sample t-test or, if assumptions of normality is not confirmed (by Kolmogorov-Smirnov test), two-sample Mann-Whitney U test.

In case of different units of measure considered for the same laboratory parameter, all values will be converted

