9.1 Variable derivation

Table 7: Variable derivation rules

Parameter	Derivation
ARDS Severity classification based on PaO₂/FiO₂	
According to PaO₂/FiO₂ (RESPIRATORY PARAMETERS form) the classification is:
 
 • if $200 \leq \text{PaO}_2/\text{FiO}_2 < 300$ mmHg then ARDS Severity=Mild • if $100 \leq \text{PaO}_2/\text{FiO}_2 < 200$ mmHg then ARDS Severity=Moderate • if $\text{PaO}_2/\text{FiO}_2 < 100$ mmHg then ARDS Severity=Severe
Worsening based on PaO₂/FiO₂	
A patient with ARDS ($\text{PaO}_2/\text{FiO}_2 < 300$ mmHg) is considered “Worsened” in case of a decrease of PaO₂/FiO₂ of at least one third (-33,3%) from the baseline PaO₂/FiO₂ value.

Oxygen Delivery System Classification based on type of oxygen support	
According to Type of oxygen support (RESPIRATORY PARAMETERS form) the classification is:
 
 • If “Invasive Medicinal Ventilation” or “ECMO” then Class=Invasive • Else if “High Flow Nasal Cannula” or “BIPAP or CPAP” then Class=High Flow • Else if “Nasal Cannula” or “Mask” then Class=Low Flow
Worsening based on Oxygen Delivery System Classification	
A patient is considered “Worsened” after baseline if he/she increase the level of severity within the oxygen delivery system classification (Invasive > High Flow > Low Flow).

Last available date (for censoring time-to-event analysis)	
Last date will be considered as the most recent dates collect in:
 
 • Last assessment, • Start and stop dates of AEs 
Last date = max (date of last assessment, start AEs, Stop AEs)

Parameter	Derivation

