Composite endpoint of phase 2 and Time to event (days) using Oxygen Delivery System Classification	
From ADDITIONAL INFORMATION form:
 
 • if “Has the patient been admitted to the ICU?” = “Yes”, then component1 = “Yes” and date of event1 = Date of Visit • if “Has the patient been admitted to the ICU?” = “No”, then component1 = “No” 
From PATIENT STATUS form:
 
 • if “Is the subject eligible to switch to rescue medication?” = “Yes”, then component2 = “Yes” and date of event2 = Rescue treatment start date 
 ○ If Rescue treatment start date is missing, then Date of Visit will be used • if “Is the subject eligible to switch to rescue medication?” = “No”, then component2 = “No” 
From ADDITIONAL INFORMATION and MECHANICAL VENTILATION forms:
 
 • If “Has the patient been mechanically ventilated?” = “Yes” and type = “Invasive mechanical ventilation”, then component3 = “Yes” and date of event3 = mechanical ventilation start date 
 ○ If mechanical ventilation start date is missing, then Date of Visit will be used • If “Has the patient been mechanically ventilated?” is not empty and type ≠ “Invasive mechanical ventilation”, then component3 = “No” 
From “Worsening based on Oxygen Delivery System Classification” (see above):
 
 • if a patient is classified as “Worsened”, then component4 = “Yes” and date of event4 = Date of Visit • if a patient is classified as not “Worsened” (excluding missing classification), then component4 = “No” 
The composite endpoint is equal to “Yes” if at least one post-baseline component (1-4) is equal to “Yes” and the date of event is the corresponding date of event. In case of more component equal to “Yes”, the first date will be used.
 
Otherwise, if all component (1-4) are equal to “No” the composite endpoint will set as “No”. The date of event will be last date where is known that all components are equal to “No”.
 
Time to composite endpoint (days) = Date of event - Date of randomization

Time from randomization to discontinuation (days)	Time from randomization to discontinuation (days) = Date of study withdrawal – Date of randomization
Extent of exposure (days)	Extent of exposure (days) = Date of last drug administration - Date of first drug administration

Parameter	Derivation

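### SAP Table 7 has no class for room air or for PaO2/FiO2 of 300 mmHg or more, which can distort the by-class percentages and, in the secondary oxygen-delivery composite, censor weaned patients early

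*SAP*

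**What the plan says.** The following places bear on the point.

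- **SAP 9.1, Table 7, oxygen delivery.** Invasive covers invasive ventilation or ECMO, and High Flow covers high-flow cannula, BIPAP or CPAP. The last branch, nasal cannula or mask, ends "then Class=Low Flow". Nothing follows for a patient on no support.
- **SAP Table 7, PaO2/FiO2.** The mildest branch, 200 to below 300, ends "mmHg then ARDS Severity=Mild". Nothing is defined at 300 or more.
- **SAP Table 7, oxygen worsening.** The patient must "increase the level of severity within the oxygen delivery system classification (Invasive > High Flow > Low Flow").
- **SAP 7.2.2.5.** The by-visit table covers these classes only: "Invasive, High Flow, or Low Flow for the type of support) will be provided".
- **SAP 4.8.** Missing data get their own category, but "Missing values will not be included in the denominator count when computing percentages".
- **SAP 7.2.2.1 with Table 7, composite using the oxygen classification.** Component 4 is 'No' only when the classification is not missing. For an event-free patient, "The date of event will be last date where is known that all components are equal to" 'No'.
- **SAP Table 7, phase 2 primary composite.** Component 4 uses a different rule. A patient with ARDS (below 300) has worsened "in case of a decrease of PaO₂/FiO₂ of at least one third (-33,3%) from the baseline PaO₂/FiO₂ value".
- **Protocol 5.2.** One entry route is "Respiratory distress, RR ≥ 30 breaths/min without oxygen".

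**The concern.** Recovery moves patients off the mild end of both scales, and neither scale has a place for them there. The natural result in a program is a blank, and the SAP then treats a blank in two ways that matter.

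First, the by-class percentages lose recovered patients from the denominator. At most they appear in a 'Missing' row, mixed with patients who were not assessed. The arm with more recovery has its severe-class shares raised more.

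Second, in the oxygen-delivery composite a weaned patient no longer has a known component 4 and is dated back to the last visit on oxygen. This censoring is informative, because weaned patients should be at lower later risk. It also depends on what happens next: a later ICU admission or intubation in the same patient still counts at its own date, whereas staying well means censoring at the earlier visit.

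The gap also acts at entry. A patient on no oxygen at baseline has no starting level, so a first nasal cannula is not an increase, although it is the plainest case of a new oxygen requirement.

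**Working it through.** **1. The plan's own figure.** SAP 3.2 expects 46 events from about 48 subjects (2:1, so 32 and 16), with times of 2 days (control) and 5 days (reparixin) and 21 days of follow-up. Reading those times as exponential medians:

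16 × (1 − 2^(−21/2)) + 32 × (1 − 2^(−21/5)) = 15.99 + 30.26 = 46.2 events.

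This reproduces. It also means that, on the planning assumptions and with no recovery, only about 1.8 of 48 patients are event-free at day 21, so almost nobody could be affected. The problem grows with the number of patients who recover, and the plan gives no rate for that. Every rate below is therefore an assumption.

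**2. By-class percentages.** If a share r of an arm is unclassified and coded missing, each reported class share is the true share divided by (1 − r). The factor is 1.33 at r = 25%, 2.00 at r = 50% and 2.67 at r = 62.5%.

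| Assumed counts | True invasive share | Share by the SAP rule |
|---|---|---|
| Reparixin: 3 of 32 invasive, 20 on room air | 3/32 = 9.4% | 3/12 = 25.0% |
| Control: 3 of 16 invasive, 6 on room air | 3/16 = 18.8% | 3/10 = 30.0% |
| Reparixin: 4 of 32 invasive, 16 on room air | 4/32 = 12.5% | 4/16 = 25.0% |
| Control: 3 of 16 invasive, 4 on room air | 3/16 = 18.8% | 3/12 = 25.0% |

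In the first pair the control-to-reparixin ratio shrinks from 2.0 to 1.2. In the second pair the difference disappears.

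**3. Early censoring in the oxygen-delivery composite.** Take constant daily hazards e (event) and c (recovery), with recovered patients staying event-free.

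- Kept as 'No' to day 21, the event proportion is e/(e + c) × (1 − exp(−21(e + c))). With e = 0.05 in both arms and c = 0.10 vs 0.05, this is 0.333 × 0.957 = 32% for reparixin and 0.5 × 0.878 = 44% for control.
- Censored exactly at recovery, Kaplan-Meier estimates 1 − exp(−21e) = 1 − exp(−1.05) = 65% in both arms.
- Dating back to the previous visit pushes the estimates further up. This was simulated with 1,500 runs of 48 patients, visits at days 1, 2, 7 and 21, events dated exactly, and one log-rank test at one-sided 0.024.

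| Event hazard (reparixin, control) | Recovery hazard (reparixin, control) | Day-21 events, kept as 'No' | Day-21 events, censored at last visit before recovery | Power, kept | Power, censored |
|---|---|---|---|---|---|
| 0.05, 0.05 | 0.10, 0.05 | 32% vs 44% | 80% vs 73% | 12% | 2% |
| 0.04, 0.08 | 0.12, 0.06 | 24% vs 54% | 76% vs 88% | 54% | 18% |
| SAP medians of 5 and 2 days | 0.10, 0.05 | 58% vs 87% | 97.8% vs 99.5% | 74% | 62% |

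Average follow-up lost is 6 to 11 days per patient. In the first row the direction of the comparison reverses.

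**4. Conflict between censoring dates.** The composite derivation uses the last date on which all components are known to be 'No'. SAP 4.1 uses study discontinuation or termination. Table 7 also defines a last available date as the latest of the last assessment and the AE dates. For a weaned patient who completes follow-up, the last two fall later than the first.

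**5. The primary composite.** The one-third fall can be computed at any PaO2/FiO2. A value of 300 or more can be a fall of one third only if baseline was at least 300 ÷ (2/3) = 450. For anyone below 450 at baseline, a value of 300 or more is simply not a worsening. It would become undefined only if the reference to a patient with ARDS were applied as a condition at each visit.

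**The case against.** The strongest reply is that nothing in the SAP calls these patients missing. Room air and a value of 320 are observations, and SAP 4.8 is about missing data. A programmer could reasonably code a weaned patient as not worsened, and the later dates in SAP 4.1 and the last-available-date rule would then apply. This stands in part: 'missing' is the likely coding result, not a stated rule. But the composite derivation provides explicitly for a missing classification, and Table 7 gives these patients no class. Two defensible codings lead to different results, so the SAP should choose one.

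A reader might infer that recovery disappears from the trial's analysis. It does not. SAP 7.2.2.2 analyses improvement of at least two points or live discharge, on a score that (protocol section 3) has a level for hospitalized patients not needing oxygen. SAP 7.2.2.9 analyses PaO2/FiO2 as continuous with no ceiling, and 7.2.2.6 compares the incidence of mechanical ventilation separately.

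The entry-without-oxygen case may be rare or empty. SAP 4.9 expects all patients to be on oxygen already, and the protocol phrase may describe how the respiratory rate is measured. That is fair. However, SAP 5.8 still records oxygen at baseline as yes or no, and 4.9 says nothing about later weaning.

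Finally, the examples in the working are constructed. That is correct; they show mechanism and direction, not an expected size.

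**Conclusion.** The point stands in a limited form and should be corrected. Both classifications lack a recovered class. If unclassified patients are coded as missing, the by-class percentages in 7.2.2.5 are inflated by 1/(1 − r), more in the arm with more recovery. In the oxygen-delivery composite, read literally, weaned patients are censored early and informatively, in conflict with two other dating rules, and a start of low-flow oxygen from none is not counted.

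Two stronger readings are not supported. One is that both scales cause early censoring; the Mild, Moderate and Severe classes feed no time-to-event derivation. The other is that the phase 2 primary result or the decision to go to phase 3 is compromised. The primary composite uses the relative fall in PaO2/FiO2, the affected composite is secondary, and SAP 7.1.3.1 rests the decision to proceed on the primary analysis alone. For the primary endpoint there is only the question of whether the ARDS condition is read visit by visit.

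The size is unknown. It ranges from almost nothing, if few patients are weaned before an event, to the shifts shown above under assumed recovery rates.

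**What to change.** In SAP Table 7, 7.2.2.5 and 4.1:

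- Add a class 'None (room air)' below Low Flow, and a class for PaO2/FiO2 of 300 mmHg or more, better than Mild.
- Count both in the 7.2.2.5 denominators, and keep 'Missing' for patients who were not assessed.
- Define oxygen-delivery worsening as any post-baseline move up in None < Low Flow < High Flow < Invasive. This also covers patients on no oxygen at baseline.
- Set component 4 of the oxygen-delivery composite to 'No' for every assessed patient who has not moved up.
- State that a PaO2/FiO2 of 300 or more counts as not worsened in the primary composite.
- State one censoring date rule, and make SAP 4.1, the last available date and the composite derivations agree with it.

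The cost is minor programming and a check that the CRF records the absence of oxygen support. The CRF is not among the documents, and Table 7 lists no such option. If it is not recorded, the state can be derived from the yes/no item on oxygen administration. No data collection or trial conduct changes. Because the trial is open-label, the change is best made and dated before database lock.

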### 4 STUDY DESIGN AND METHODOLOGY

#### 4.1 Phase 2 Study design

The study is designed for the investigational use of a CXCR1 and CXCR2 allosteric antagonist named Reparixin. It will involve 48 adult patients with severe COVID-19 pneumonia in accord with any of the following:

1. Age 18 to 90.

2. Confirmed COVID-19 diagnosis

3. At least one of the following: (1) Respiratory distress,  $RR \ge 30$  breaths/min without oxygen; (2) Partial arterial oxygen pressure (PaO2) / Fraction of inspiration O2 (FiO2) >100 <300mmHg (1mmHg = 0.133kPa).

4. Chest imaging confirms lung involvement and inflammation.

5. Inflammatory status as documented by at least one of the following: Lactate dehydrogenase (LDH) > normal range, C-reactive protein (CRP)  $\geq$  100mg/L or IL-6  $\geq$  40pg/mL, serum ferritin  $\geq$  900ng/mL, XDP >20mcg/mL.

Patients randomized to the active treatment will receive an oral dose of reparixin (1200 mg tablets TID) for 7 days. In case of improvement, treatment can be prolonged at discretion of the investigator up to a total of 21 days of treatment. Patients randomized to the both arms will be offered, in case of worsening (e.g. need of ICU and/or mechanical ventilation), a rescue medication based on their physicians' judgement, without any constrain from the sponsor.

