### 9.4.2 Analysis of efficacy variables

#### 9.4.2.1 Primary analysis of phase II

In phase II, the primary endpoint to assess the efficacy of Reparixin versus the Control is the time freedom from a composite endpoint of events including supplemental oxygen treatment, mechanical ventilation use, admission to ICU, and any use of rescue medication. The time to the first event (any one of the components defined in the phase II composite endpoint) will be used for analysis. In case of no events, the rules for censoring defined in section 9.4.1 will be used.

The primary endpoint will be evaluated by means of Kaplan-Meier estimates and log-rank test. The null hypothesis H0phaseII is that the freedom form events in Reparixin (TREPARIXIN) is lower or equal than control (TCONTROL):

H0phaseII: TREPARIXIN ≤ TCONTROL H1phaseII: TREPARIXIN > TCONTROL

where TREPARIXIN and TCONTROL are the freedoms from event for Reparixin and Control, respectively. The null hypothesis H0phaseII will be rejected, and superiority of Reparixin concluded (alternative hypothesis H1phaseII) if log-rank p-value will be lower than pre-specified threshold, depending at which analysis (interim or final) the test is performed. Thresholds are calculated according to O'Brien-Fleming spending function boundaries and tare reported in Table 1.

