#### 9.4.2.2 Primary analysis of phase III

In case of rejection of the null hypothesis H0phaseII, the primary endpoint to assess the efficacy of Reparixin versus the Control in phase III is the time freedom from a severe composite endpoint of events including death, admission to the ICU, mechanical ventilation. The time to the first severe event (any one of the components defined in the phase III composite endpoint) will be used for analysis. In case of no events, the rules for censoring defined in section 9.4.1 will be used.

The primary endpoint will be evaluated by means of Kaplan-Meier estimates and log-rank test. The null hypothesis  $H_{0phaseIII}$  is that the freedom form severe events in Reparixin ( $\Pi_{REPARIXIN}$ ) is lower or equal than control ( $\Pi_{CONTROL}$ ):

H0phaseIII:  $\Pi_{\text{REPARIXIN}} \leq \Pi_{\text{CONTROL}}$ H1phaseIII:  $\Pi_{\text{REPARIXIN}} > \Pi_{\text{CONTROL}}$ 

where  $\Pi_{\text{REPARIXIN}}$  and  $\Pi_{\text{CONTROL}}$  are the freedoms from severe event for Reparixin and Control, respectively.

The null hypothesis H0phaseIII will be rejected, and superiority of Reparixin concluded (alternative hypothesis H1phaseIII) if log-rank p-value will be lower than pre-specified threshold, depending at which analysis (interim or final) the test is performed. Thresholds are calculated according to O'Brien-Fleming spending function boundaries and tare reported in Table 2.

Primary endpoint of phase 3 will be tested only if superiority of Reparixin is shown in phase 2.

Both null hypotheses H0phaseII and H0phaseIII must be rejected in order to claim superiority on Reparixin over Standard of Care. Consequently, no multiplicity correction of type I error will be applied on primary endpoints.

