Composite endpoint of phase 2 and Time to event (days)	
From ADDITIONAL INFORMATION form:
 
 • if “Has the patient been admitted to the ICU?” = “Yes”, then component1 = “Yes” and date of event1 = Date of Visit • if “Has the patient been admitted to the ICU?” = “No”, then component1 = “No” 
From PATIENT STATUS form:
 
 • if “Is the subject eligible to switch to rescue medication?” = “Yes”, then component2 = “Yes” and date of event2 = Rescue treatment start date 
 ○ If Rescue treatment start date is missing, then Date of Visit will be used • if “Is the subject eligible to switch to rescue medication?” = “No”, then component2 = “No” 
From ADDITIONAL INFORMATION and MECHANICAL VENTILATION forms:
 
 • If “Has the patient been mechanically ventilated?” = “Yes” and type = “Invasive mechanical ventilation”, then component3 = “Yes” and date of event3 = mechanical ventilation start date 
 ○ If mechanical ventilation start date is missing, then Date of Visit will be used • If “Has the patient been mechanically ventilated?” is not empty and type ≠ “Invasive mechanical ventilation”, then component3 = “No” 
From “Worsening based on PaO₂/FiO₂” (see above):
 
 • if a patient is classified as “Worsened”, then component4 = “Yes” and date of event4 = Date of Visit • if a patient is classified as not “Worsened” (excluding missing classification), then component4 = “No” 
The composite endpoint is equal to “Yes” if at least one post-baseline component (1-4) is equal to “Yes” and the date of event is the corresponding date of event. In case of more component equal to “Yes”, the first date will be used.
 
Otherwise, if all component (1-4) are equal to “No” the composite endpoint will set as “No”. The date of event will be last date where is known that all components are equal to “No”.
 
Time to composite endpoint (days) = Date of event - Date of randomization

Parameter	Derivation

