Time to supplemental oxygen requirement (days)	Time to supplemental oxygen requirement (days) = First Administration start date - Date of randomization
Time to mechanical invasive ventilation use (days)	Time to (invasive) mechanical ventilation use (days) = First (invasive) Mechanical Ventilation start date - Date of randomization
Time to admission to ICU (days)	Time to admission to ICU (days) = Admission date - Date of randomization
Time to rescue medication (days)	Time to rescue medication (days) = First rescue treatment start date - Date of randomization
Overall survival (days)	Overall survival (days) = Date of death - Date of randomization
Subject with improvement based on Likert scale	Improvement = any of these answers: 
 • 1 = minimally better, • 2 = moderately better, and • 3 = markedly better
Cumulative quantity (L) of oxygen treatment	Cumulative quantity of oxygen treatment (L) = Sum of all Quantity (L) in CONCOMITANT OXYGEN TREATMENT form, from randomization to time point of interest. It is defined as supplemental oxygen requirement any increased used of oxygen compared to baseline.
Cumulative duration (hours) of oxygen treatment	Cumulative duration of oxygen treatment (hours) = Sum of duration of oxygen administration (hours) in CONCOMITANT OXYGEN TREATMENT form, from randomization to time point of interest. Duration of oxygen administration (hours) = Administration end date/time - Administration start date/time / 60
Cumulative duration (hours) of mechanical ventilation	Cumulative duration of mechanical ventilation (hours) = Sum of duration of mechanical ventilation (hours) in MECHANICAL VENTILATION form, from randomization to time point of interest. Duration of mechanical ventilation (hours) = End date/time - Start date/time / 60
Duration (days) of ICU stay	Duration of ICU stay (days) = Discharge date - Admission date
Change from baseline	For changes from baseline the baseline value will constitute the minuend and the later value the subtrahend.
Conversion of Time Intervals	If a time interval was calculated in minutes, hours or days and needs to be converted into months or years the following conversion factors will be used: 
 • 1 hour = 60 minutes • 1 day = 24 hours • 1 week = 7 days • 1 month = 30.4375 days • 1 year = 365.25 days

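### SAP Table 7 dates ICU admission at the recording visit in all four composite rows, so time to first event can fall later than its own ICU component

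*SAP*

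**What the plan says.** The protocol defines both primary analyses by the earliest component. For phase 2 (9.4.2.1): "The time to the first event (any one of the components defined in the phase II composite endpoint) will be used for analysis". For phase 3 (9.4.2.2): "The time to the first severe event (any one of the components defined in the phase III composite endpoint) will be used for analysis".

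SAP 9.1, Table 7, turns this into derivation rules. Four rows build a composite: the phase 2 primary endpoint, its modified version with death added, the phase 3 primary endpoint, and the phase 2 composite using the oxygen delivery classification. In each row a positive ICU answer sets the component to yes "and date of event1 = Date of Visit", with no mention of the admission date. In the same rows invasive ventilation is scored "and date of event3 = mechanical ventilation start date", and the visit date serves only when that start date is missing. When several components are positive, "the first date will be used".

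Later in Table 7 the admission date is used twice: "Time to admission to ICU (days) = Admission date - Date of randomization" and "Duration of ICU stay (days) = Discharge date - Admission date".

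**The concern.** The SAP treats the ICU admission date as available but does not use it where the primary endpoint is built. ICU status is recorded at scheduled visits, and after Day 2 these are only Week 1, End of treatment and End of follow up (SAP Table 1). An admission between visits can therefore be dated days after it happened. The assumed median times to event are only 2 to 8 days (SAP Table 2), so such a delay is not small against the time scale.

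These rows define the primary endpoint of both phases, and SAP 7.1.3.1 rests the decision to go on to phase 3 on the primary analysis alone. The inconsistency could also show in the study's own outputs: SAP 7.1.3 analyses first ICU admission separately, and Table 7 dates that time from the admission date.

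**Working it through.** **1. Dating rules in Table 7, side by side**

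| Component | Date in the composite rows | Date when derived on its own |
|---|---|---|
| ICU admission (all four rows) | visit, no alternative | admission date |
| Invasive ventilation (all four rows) | start date; visit if missing | start date |
| Rescue (three phase 2 rows) | start date; visit if missing | start date |
| Death (modified phase 2 and phase 3 rows) | date of death | date of death |

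Worsening of PaO2/FiO2 is also dated at the visit, but it is measured at the visit, so that is consistent.

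**2. What the rule does to one patient**

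Composite time = earliest derived component date − randomization date. Week 1 is taken as day 7.

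- Admitted day 3, recorded day 7, nothing else dated: ICU time 3, composite time 7, delay 7 − 3 = 4 days.
- The same patient ventilated invasively on day 4: composite time min(7, 4) = 4, delay 1 day.
- Phase 3, admitted day 8, died day 12, no visit or invasive ventilation between: composite time 12, ICU time 8, delay 4 days.

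**3. The plan's own figures**

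Expected events in 21 days (SAP 3.2) = Σ n × (1 − 0.5^(21/median)).

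- Phase 2, 16 control and 32 reparixin, medians 2 and 5 days: 16 × 0.9993 + 32 × 0.9456 = 46.2. The SAP plans 46.
- Phase 3, 37 and 74, medians 2 and 4 days: 37 × 0.9993 + 74 × 0.9737 = 109.0. The SAP plans 109.

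Simulating the sequential design with the boundaries of SAP Tables 4 and 5 gives power 0.802 in phase 2 (hazard ratio 2/5 = 0.40) and 0.903 in phase 3 (2/4 = 0.50). This matches the stated 80% and the protocol's 90%. The planned figures are not in dispute.

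**4. Size of the loss**

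The documents give no share of first events that are ICU admissions, no fixed End of treatment day and no timing of later components. These are assumed:

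- Schedule A: days 1, 2, 7, 14. This is seven days of treatment plus about seven of follow-up (protocol summary). Protocol 4.1 extends treatment only for improvers: "In case of improvement, treatment can be prolonged at discretion of the investigator up to a total of 21 days of treatment".
- Schedule B: days 1, 2, 7, 21, 28.
- ICU share of first events: 10 to 40% in phase 2, with PaO2/FiO2 worsening a further 25%; 20 to 70% in phase 3.
- Exponential times rounded up to the day; 20,000 trials per scenario; one-sided log-rank test at the final boundary (0.024 in phase 2, 0.02151 in phase 3); interims ignored.

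Loss = power with ICU dated at admission − power as written, in percentage points. Each range runs from the lowest to the highest ICU share.

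| Scenario | A: no same-day dated component | A: 80% have one | B: no same-day dated component | B: 80% have one |
|---|---|---|---|---|
| Phase 2, 2 vs 5 days | 1.2–3.7 | 0.2–0.9 | 1.7–5.0 | 0.4–1.8 |
| Phase 3, 2 vs 4 days | 2.6–6.8 | 0.3–1.7 | 5.5–10.7 | 1.1–3.9 |
| Phase 3, 4 vs 8 days | 1.0–2.7 | 0.1–0.6 | 3.2–7.6 | 0.7–2.3 |

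Power with the fix is 77.9%, 90.8% and 86.3% under A, and 75.3%, 91.3% and 91.1% under B. If PaO2/FiO2 worsening is 50% of phase 2 first events, the loss is at most 1.3 points (A) or 1.6 (B). In phase 3 at 2 vs 4 days under A, with no same-day component, the reparixin median reads 5.2 to 6.9 days as written against 4.5 with the fix.

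**5. Why every column is an upper bound**

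These runs remove the delay only when another component is dated on the admission day. Under the first-date rule, a ventilation, rescue (phase 2) or death (phase 3) date between admission and visit also shortens it. With an assumed median lag of 2 days to such a component, and none on the same day, the largest losses fall to 0.7–1.4 points in phase 2 under A (40% ICU), 2.4–3.1 in phase 3 at 2 vs 4 days under A (70% ICU), and 3.4–4.3 for the same phase 3 case under B. Ranges are over repeat runs.

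**6. Type I error, with equal ICU shares in both arms**

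Phase 2: 2.88–3.14% as written, 3.10–3.12% fixed. Phase 3: 2.43–2.53% as written, 2.48–2.62% fixed. Phase 2 exceeds its nominal 2.4% even with every date exact (3.13–3.28%), so the excess does not come from the ICU rule.

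**The case against.** **The effect may be small.** The strongest form of this argument concerns phase 2. Need for ICU is itself an example of the worsening that leads to an offer of rescue (protocol summary and 4.1), and rescue takes its own start date in the same row. Many ICU-first patients would then have a second date close to admission. This stands: it makes a loss near the upper bound unlikely in phase 2. It does not make the derivation right.

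**The schedules are assumed.** Neither reproduces the 21 days of efficacy follow-up in the protocol summary and SAP 3.2, and the case report form, which might show extra visits, is not among the documents. This also stands. The power figures indicate scale and are not predictions.

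**Phase 3 is provisional.** SAP 4.7 foresees a protocol amendment and SAP update before phase 3. The row can be corrected then, but only if someone notices it; otherwise the rule carries forward.

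**Stronger readings that the documents do not support.**

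- A reader might infer that, in an open-label trial, late dating favours reparixin or inflates the false-positive rate. The rule is the same in both arms. Bias would need the visit-dated share or the visit timing to differ by arm, and nothing in the documents shows that.
- A reader might also call the rescue component wrong, because the three phase 2 rows score eligibility to switch, while protocol 9.4.2.1 and SAP 3.5.1 and 7.1.3.1 speak of use. Yet protocol section 3 and SAP 3.5.1 also speak of what the patient requires, protocol 9.1 of requirement, and SAP 5.4 summarises patients switching. The form item may simply record switching. This is not part of the claim.

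**Conclusion.** The inconsistency is certain from the text. Table 7 dates ICU admission at the visit in four rows, uses the admission date twice elsewhere, and so departs from the protocol's time to first event. It affects patients whose first event is an ICU admission between visits with no other dated component before the visit.

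The consequence is late and tied event times, longer reported medians and some loss of power. Under the ICU shares assumed above, the loss is at most about 4 points in phase 2 and 7 in phase 3 with visits on days 1, 2, 7 and 14, and about 5 and 11 with visits on days 1, 2, 7, 21 and 28. In phase 2 it is probably well below the bound. Confidence is high in the inconsistency and low in any single power figure. It should be fixed, but it does not threaten the validity of a positive result.

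**What to change.** In all four composite rows of Table 7, set the ICU event date to the admission date and fall back on the visit date only when the admission date is missing, as is already done for ventilation. Carry the same rule into any phase 3 SAP update. Leave PaO2/FiO2 worsening at the visit date.

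The cost is SAP wording and programming before database lock. Table 7 already draws on the admission date, though its collection should be confirmed against the case report form. This change alone alters when an event is dated, not what counts as one.

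If the sponsor also states that only admissions after randomization count, that should be declared in SAP 4.9. ICU status is recorded at baseline too (SAP 5.8), so the clause can change who scores an event.

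Separately, the sponsor should check what the rescue item on the form records and reconcile the passages on eligibility, requirement and use. No default is proposed here.
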